**Figure 1. Study Schematic**

The intensive PK portions of Part 1 and Part 2 will allow enrollment of pediatric subjects with or without compensated cirrhosis who are treatment naïve and who meet the weight bands for their age (Table 11). The HCV genotype must be identified (i.e., Screening laboratory result indicating HCV genotype 1, 2, 3, 4, 5, or 6-infection) for those participating in the intensive PK portions of the study. The safety/efficacy portion of both Part 1 and Part 2 will include pediatric patients with or without compensated cirrhosis that are treatment naïve or treatment experienced (prior IFN [alpha, beta or pegIFN], RBV or SOF exposure), with or without HIV-1 co-infection, or subjects with mixed or indeterminate HCV genotype.

Pediatric subjects that fall outside of the weight bands for their age (Table 11) may be included in the safety and efficacy parts of Part 1 and Part 2 only with approval of the AbbVie Therapeutic Area Medical Director after consideration of risks and benefits. All

subjects will receive GLE/PIB for 8, 12 or 16 weeks, depending on their HCV genotype, cirrhosis and prior HCV treatment status. No dose adjustments of GLE/PIB will be made as a consequence of weight change during the Treatment Period. For patients with an indeterminate or mixed genotype including GT3, treatment duration will default to the respective GT3 duration based upon treatment-experience and cirrhosis status. Patients with a mixed GT other than GT3, treatment duration will default to the longer treatment duration based on GT, treatment-experience and cirrhosis status.

Both Parts 1 and 2 will consist of a Screening Period (Section 5.1.1), a Treatment Period (Section 5.1.2), and a Post Treatment Period (Section 5.1.3). Subjects who prematurely discontinue during the Treatment Period in Part 1 or Part 2 will be followed-up in the Post-Treatment Period through Week 144. After completing the Treatment Period in Part 1 or Part 2, the subjects will be followed-up for 144 weeks in the Post-Treatment Period. Subjects who prematurely discontinue from the Post-Treatment Period will be discontinued from the study.

The pharmacokinetic and clinical data from age groups of 3 to < 6, 6 to < 9, and 9 to < 12 years old may be combined for final analyses if exposures from these three (3) age groups are comparable to each other.

In both Parts 1 and 2, for each of the analytes (GLE and PIB), the geometric mean and individual AUC values from these pediatric subjects from the Week 2 intensive PK sampling will be compared with the distribution of individual AUCs across Phase 2/3 studies in adults on an ongoing basis. Dose adjustments may be made for each component of the DAA regimen if the respective geometric mean AUC in pediatric subjects is significantly deviated from the geometric mean AUC values in adults.

AUC will be the primary measure for dose adjustment. Other pharmacokinetic exposure parameters including  $C_{\max}$  and  $C_{\text{trough}}$  will be considered to provide similar therapeutic exposures that have been safe and efficacious in adult subjects.

Additional safety and efficacy criteria may be considered for making dose adjustment decisions for Parts 1 and 2 to ensure safe and efficacious exposures.

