### **GLE/PIB Dose Selection Strategy for the Pediatric Population**

AbbVie's pediatric formulation development strategy is to develop a dosage form that provides suitable and flexible dosing across the pediatric age range of 3 to < 18 years. Development of a suitable pediatric formulation was guided by considerations of solubility, dose flexibility, stability, compatibility, and ease and reliability of the manufacturing process. It is likely the adult tablets will be suitable for adolescent subjects 12 years of age and older with weights  $\geq 45$  kg. This population is able to swallow tablets and utilizing the adult tablet would enable earlier enrollment of this population. In Part 1 of Study M16-123, a total of 47 adolescent subjects received daily administration of GLE/PIB 300 mg/120 mg. PK results showed that the exposures of GLE and PIB in HCV-infected adolescent subjects (12 to < 18 years of age) were similar to the exposures observed in HCV-infected adult subjects following administration of GLE/PIB 300 mg/120 mg.

GLE and PIB exhibit low aqueous solubility. Due to probable requirement of solvent(s) that are undesirable for pediatric patients for any oral solution, and [REDACTED]

[REDACTED] AbbVie developed a pediatric formulation based on the solid oral formulations used to manufacture the adult tablets.

[REDACTED]

To provide exposures in pediatric subjects comparable to adult exposures using the pediatric formulation, the GLE and PIB dose in pediatric patients of 3 to < 12 years of age were revised from originally proposed doses. Preliminary PK results from the initial

proposed pediatric doses demonstrated that though GLE and PIB exposures were within the range of exposure for efficacy and safety in adults for each of the pediatric cohorts, the average exposures in each of the cohorts were lower than the targeted AUC and led to a dose adjustment. Additional subjects were enrolled and the intensive PK results obtained, and additional population PK modeling performed, confirming that the adjusted doses demonstrate exposures that would allow for bridging of adult data, using a 50/20 mg dose ratio. These doses (Table 11) are proposed to be used in the subjects enrolling in the non-IPK portion of Part 2, in order to confirm that the doses would provide similar exposures observed in HCV-infected adult subjects, close to the targeted AUC.

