**Table 11. Proposed Glecaprevir and Pibrentasvir Doses for the Pediatric Population**

Formulation	Age Group (yrs) & Weight Band (kg)	Final Proposed Doses (mg)	
		Glecaprevir	Pibrentasvir
Pediatric formulation	3 to < 6 yr 12 to < 20 kg	150	60
	6 to < 9 yr ≥ 20 to < 30 kg	200	80
	9 to < 12 yr ≥ 30 to < 45 kg	250	100
Adult formulation	12 to < 18 yr ≥ 45 kg	300	120

The doses of the pediatric formulation were adjusted based upon the intensive pharmacokinetic analysis of the first approx. 17 subjects enrolled across the age cohorts. The final proposed dosing for each age cohort has been confirmed by additional IPK analysis. These drug dose changes are included in this protocol amendment. Dose adjustments were made as necessary to ensure safe and efficacious exposures, but did not exceed the adult dose of 300/120 mg of GLE/PIB.

For Part 1, enrollment commenced with pediatric subjects ≥ 12 to < 18 years old who are ≥ 45 kg and willing to swallow the adult formulation. Part 2 enrollment initiated in pediatric subjects ≥ 3 to < 12 years old with the pediatric formulation. Based on current modeling and available PK data at the completion of the IPK portion of Part 2, the above proposed doses of the pediatric formulation are the target doses for use in children

< 12 years of age. The pharmacokinetic and clinical data will be used to confirm appropriate exposure in each of the  $\geq 3$  to < 12 years old age groups.

Details on the dose adjustment considerations for Part 1, the enrollment sequence in Part 1, and the considerations for enrollment in Part 2 are provided in Section 5.1.

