## **8.0 Statistical Methods and Determination of Sample Size**

### **8.1 Statistical and Analytical Plans**

The analysis of pharmacokinetic endpoints will be performed when 12 subjects complete the 2 week intensive PK (IPK) measurements, and these analyses will be done within each age group. For subjects enrolled in Japan, the pharmacokinetic parameters will be summarized separately.

The efficacy, durability of response, resistance, growth and development, patient-reported outcomes, and safety analyses will be performed by age group and overall (across Parts 1 and 2 combined).

The first interim analysis will occur once all subjects participating in IPK in Part 1 complete PT Week 12 or prematurely discontinue from the study. A second interim analysis will occur once all subjects in Part 1 complete PT Week 12 or prematurely discontinue from the study. A third interim analysis will occur once all subjects participating in the IPK portion in Part 2 complete PT Week 12 or prematurely discontinue from the study. A fourth interim analysis will occur once all subjects in

Parts 1 and 2 complete PT Week 12 or prematurely discontinue the study. Final analysis will occur after the completion of the whole study.

SAS® (SAS Institute, Inc., Cary, NC) for the UNIX operating system will be used for all analyses. All statistical tests and all confidence intervals will be two-sided with alpha level of 0.05.

Safety analyses will be performed on all subjects who receive at least one dose of study drug.

Demographic and efficacy analyses will be performed on the intention-to-treat (ITT) population defined as all enrolled subjects who receive at least one dose of study drug, unless otherwise specified.

Sensitivity analyses of the SVR12 endpoint, when applicable, will be performed on the intention-to-treat population modified to exclude subjects who did not achieve SVR12 for reasons other than virologic failure (mITT-VF).

No data will be imputed for any efficacy or safety analysis except for analyses of SVR endpoints (HCV RNA data). HCV RNA values will be selected for the analyses of all SVR endpoints (e.g., SVR4, SVR12, and SVR24) based on defined statistical visit windows. A backward imputation method will be used to impute missing responses for SVR analyses. Detailed statistical methods for all endpoints will be provided in the Statistical Analysis Plan (SAP).

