## **8.2 Determination of Sample Size**

It is planned to enroll a total of approximately 125 subjects into this study. The primary endpoint will be steady state AUC of GLE and PIB. Practical considerations include the expected larger number of adolescents within this population, in comparison to the younger age cohorts.

The proposed sample size of 48 subjects (12 subjects for each age cohort) for intensive pharmacokinetic sampling (separate from sampling performed in subjects in Japan) is expected to adequately characterize the pharmacokinetics of GLE and PIB to enable dose selection in pediatric subjects.

Approximately 10 subjects will undergo additional PK sampling to support characterization of GLE and PIB exposures in children from Japan.

Additional subjects will be enrolled to reach the proposed total of 125 subjects to provide safety and efficacy information.

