10.3 Primary PK and Primary Efficacy Analysis

10.3.1 Primary PK Analysis

The primary pharmacokinetic endpoint will be the steady state AUC of GLE and PIB estimated by non-compartmental pharmacokinetic analysis or population pharmacokinetic analysis. The 95% confidence interval for the geometric mean of AUC values will be calculated. For subjects enrolled in Japan, the pharmacokinetic parameters will be summarized separately.

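### The plan bridges from adults on similar exposure but sets no pediatric/adult AUC ratio or bound, and a non-significant difference would not show similarity for glecaprevir

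*Protocol*

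**What the plan says.** Protocol Section 3.0 (dose selection strategy) reports that the adjusted doses give exposures that permit bridging of adult data. It assigns those doses to the remaining Part 2 subjects "in order to confirm that the doses would provide similar exposures observed in HCV-infected adult subjects, close to the targeted AUC". Section 5.6.4, below Table 11, adds that "The pharmacokinetic and clinical data will be used to confirm appropriate exposure in each of the" Part 2 age groups.

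Section 5.1 describes the comparison. Week 2 geometric mean and individual AUC values "will be compared with the distribution of individual AUCs across Phase 2/3 studies in adults on an ongoing basis", and a dose may be adjusted "if the respective geometric mean AUC in pediatric subjects is significantly deviated from the geometric mean AUC values in adults". AUC is the primary measure. Cmax and Ctrough "will be considered to provide similar therapeutic exposures that have been safe and efficacious in adult subjects", and safety and efficacy criteria may be added. More intensive-PK subjects may be enrolled if exposure targets are not met. The same section lets the three Part 2 age groups be combined if their exposures are comparable. None of these terms has a numeric definition.

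On analysis, Section 8.1 states: "All statistical tests and all confidence intervals will be two-sided with alpha level of 0.05". For the primary PK endpoint, SAP 10.3.1 states: "The 95% confidence interval for the geometric mean of AUC values will be calculated". Protocol Section 8.1.2.1 plans the same interval. Neither document plans a ratio to adults.

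On numbers, Section 8.2 gives "The proposed sample size of 48 subjects (12 subjects for each age cohort) for intensive pharmacokinetic sampling", without a precision target. Section 5.5.3 aims for about 22 subjects on the final dose in each Part 2 age group.

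**The concern.** A claim of similar exposure needs a statement of how large a difference would be tolerated, and an interval that rules out larger ones. The plan has neither. Its wording invites the reader to ask whether the 95% interval for the pediatric mean excludes the adult mean, and to accept similarity when it does not. With few children and a variable drug, that outcome is likely even when exposure is well below adult levels. The answer then depends on sample size and variability more than on how far exposure lies from adults. What is at stake is the support for bridging at the final doses.

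**Working it through.** **1. The plan's own figure.** The 48 intensive-PK subjects are 4 cohorts × 12. No CV, margin or precision is given, so there is nothing further to reproduce.

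**2. Variability (assumption).** The current text gives no SD. Appendix E reprints a superseded table with adult AUC percentiles. For a log-normal AUC, SD = ln(P95/P5)/(2 × 1.645).
- GLE: ln(29,000/980)/3.29 = 1.03.
- PIB: ln(3,400/590)/3.29 = 0.53.
- GLE cross-check: the same table puts 22% of adults at or below half the target AUC, which gives ln 2/0.772 = 0.90.
- GLE lower case: 20% below 1.03, which is 0.82.

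**3. Reading to be tested (assumption).** A two-sided 5% one-sample t-test on log AUC, with the adult geometric mean treated as known. The miss rate is the probability that |T| is at most the critical value, where T is noncentral t with n − 1 degrees of freedom and noncentrality |ln ratio|/(SD/√n).

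Example, GLE, SD 1.03, ratio 0.5:
- n = 12: 0.693/(1.03/3.464) = 2.33 against a critical value of 2.201; missed 43%.
- n = 22: 0.693/(1.03/4.690) = 3.16 against 2.080; missed 15%.

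**4. Miss rates.**

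| Drug, log SD | True ratio | n = 12 | n = 22 |
|---|---|---|---|
| GLE, 1.03 | 0.5 | 43% | 15% |
| GLE, 0.90 | 0.5 | 32% | 7% |
| GLE, 0.82 | 0.5 | 24% | 4% |
| GLE, 1.03 | 0.67 | 77% | 59% |
| GLE, 0.90 | 0.67 | 71% | 49% |
| GLE, 0.82 | 0.67 | 66% | 41% |
| PIB, 0.53 | 0.5 | 2% | below 1% |
| PIB, 0.53 | 0.67 | 34% | 8% |

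**5. What the planned interval can show.** The typical 95% half-width is exp(t × SD/√n). For GLE with SD 1.03 this is a factor of 1.92 at n = 12 and 1.58 at n = 22. For PIB at n = 12 it is 1.40. The data can therefore support a statement about the ratio to adults, but the plan never asks for one.

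**The case against.** The best defence is that no passage specifies a significance test on AUC. The 0.05 sentence in Protocol 8.1 is a general convention, the PK plan is one of estimation, and SAP 10.2 disclaims hypothesis testing (for efficacy endpoints only). This stands: the miss rates describe one reading, and a reader who took 43% as a property of the trial would go beyond the documents. If the word is not statistical, however, the rule has no definition at all, and the gap is the same.

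A reader might also infer that the sponsor accepts low exposure whenever it lies inside the wide adult range. Section 3.0 points the other way: average exposures were below target although within that range, and this led to a dose adjustment. No passage makes the adult 5th to 95th percentiles an acceptance band. Nor does any passage apply a significance rule to pooled Part 2 data, so a charge that pooling would flag trivial differences has no basis.

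The geometric mean is not the sole basis either. Individual AUCs, Cmax, Ctrough, safety, efficacy and population PK also count, though none has a numeric limit. Finally, Section 5.6.4 reports that the doses were adjusted and then confirmed by further intensive PK, so n = 12 is largely past. That is fair, and n = 22 is the relevant size for what remains. Confirmation at the final dose is still required there, and the criterion is still absent.

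**Conclusion.** The concern holds in this form: neither document defines what would make pediatric exposure similar to adult exposure, and the planned primary PK analysis cannot supply the answer. That conclusion comes from the text alone.

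The size is conditional. It rests on the t-test reading, on log SDs taken from superseded text, on a known adult mean, and on every AUC being treated as directly observed. Final-dose subjects outside intensive sampling will have model-based AUCs from sparse samples. At the 22 per group still ahead, gross under-exposure to GLE would usually be detected. A one-third reduction would be missed about as often as it was found. The problem is mainly one for GLE; for PIB it is small at a halved exposure. The documents do not show that any dose was confirmed on the strength of a non-significant result.

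**What to change.** In SAP 10.3.1, for GLE and PIB, by age group at the final dose, report the pediatric/adult geometric mean AUC ratio with its 95% interval. Describe exposure as similar to adults only when the interval lies within bounds that the sponsor fixes before the final-dose data are analysed. Otherwise report the ratio and the deviation that the interval cannot exclude. Use the same form to judge whether the Part 2 age groups are comparable before combining them. The wording in Protocol 5.1 on exposure targets and on deviation from adults should be reconciled with this analysis. No dose-adjustment rule is proposed here.

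The cost is SAP text and one table from data already collected, with no extra subjects or samples. The drawback is that a single age group may not carry the GLE claim alone. With bounds of 0.5 to 2, used purely for illustration, and a true ratio of 1, simulation puts the GLE interval inside the bounds as follows:
- n = 22: about 71% (SD 1.03) to 86% (SD 0.90).
- n = 12: only about 22% to 39%.

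PIB exceeds 99% at n = 22. At a true ratio of 0.5, similarity would be wrongly claimed about 2.5% of the time or less.

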### **5.1.1 Screening**

Prior to any study specific procedures being performed on the subject at the Screening Visit for Part 1 or Part 2, parent(s)/guardian(s) must provide written (signed and dated) informed consent and the subject must provide assent (as appropriate for age and country) respectively.

Subjects will receive a unique subject number via the Interactive Response Technology (IRT) system and will undergo the study procedures identified in Section 5.3.1 associated with the Screening Visit. The investigator or his/her designated and qualified representatives will evaluate whether the subject meets all of the eligibility criteria specified in Section 5.2.1 and Section 5.2.2 for the Part in which they are enrolling during the period from the Screening Visit through Study Day 1 prior to dosing and record the results of this assessment and the details of the informed consent and assent process in the subject's medical records.

Eligible subjects have up to 42 days following the Screening Visit to enroll into Part 1 or Part 2 of the study.

#### **5.1.1.1 Rescreening**

Subjects who at Screening have any of the following are not eligible to retest or rescreen:

- A positive Hepatitis B surface antigen (HBsAg);
- Hepatitis B DNA > lower limit of quantitation (LLOQ);
- A positive serum pregnancy test (if female).

Otherwise, subjects may be retested or rescreened only once before requiring approval from the Primary Therapeutic Area Medical Director to rescreen again.

Retesting:

Subjects who have exclusionary laboratory parameter(s) per Exclusion Criterion 8 (Section 5.2.2) are allowed to retest on the related panel(s) (e.g., exclusionary albumin requires a repeat chemistry panel) within the same screening period and must meet all other eligibility laboratory criteria on the panel that is repeated. If the retest result(s) are also exclusionary, the subject may only be rescreened or retested again with approval from the Primary Therapeutic Area Medical Director.

#### Rescreening:

Subjects that exceed the initial 42-day screening period should be rescreened for all laboratory and eligibility criteria, not just those that were exclusionary at the first screening attempt (with the exception of HBsAg, Hepatitis B virus (HBV) DNA, and positive serum pregnancy test) (Section 5.2.2).

The Primary Therapeutic Area Medical Director should be contacted for approval prior to rescreening. Subjects that are beyond the initial 42-day screening period may still be allowed to enroll within a reasonable time period if they continue to meet all eligibility criteria and have received approval by the Primary Therapeutic Area Medical Director. If rescreened, the 42 day screening period restarts, and subjects retain their initial subject number.

For subjects who rescreen and still do not meet the study eligibility criteria upon retest/rescreen, the site personnel must register the subject as a screen failure in both IRT and electronic data capture (EDC) systems.

### **5.1.2 Treatment Period (TP)**

After meeting all the eligibility criteria, subjects will be enrolled to a study regimen according to their genotype, cirrhosis and prior HCV treatment status as shown in Table 5. for global subjects and Table 6 for subjects in Japan. The treatment duration for subjects in Japan is consistent with the currently proposed label in Japan. There are some minor differences from the Global regimen, mostly in subpopulations not common in Japan

(e.g., GT5 and 6) after review of the Japan specific Registrational program, consisting of majority GT1 and 2.

**Table 5. Treatment Regimen and Duration (Excluding Subjects in Japan)**

Patient Population	Duration
GT1 – 6 NC, TN GT1, 2, 4 – 6 NC, TE	8 weeks
GT1 – 6 C, TN GT1, 2, 4 – 6 C, TE	12 weeks
GT3 TE	16 weeks

Legend: C = Cirrhotic; NC = Non-Cirrhotic; TE = Treatment experienced to IFN (alpha, beta or pegIFN) ± RBV or SOF/RBV ± pegIFN; TN = Treatment Naïve

**Table 6. Treatment Regimen and Duration (Subjects in Japan)**

Patient Population	Duration
GT1 – 2 NC, TN, TE – IFN	8 weeks
GT1 – 2 C, TN, TE – IFN GT3 – 6 NC, C, TN, TE – IFN GT1 – 6 TE – SOF	12 weeks

Legend: C = Cirrhotic; NC = Non-Cirrhotic; TE – IFN = Japan Treatment experienced to IFN (alpha, beta or pegIFN) ± RBV; TE – SOF = Japan Treatment experienced to SOF/RBV; TN = Treatment Naïve

GLE/PIB will be administered as described in Section 5.5.1 (Treatments Administered). Subjects and their parent(s)/guardian(s) will receive instructions about the study drugs at the Day 1 Visit. The study drugs will be dispensed at the visits as indicated in [Appendix C](#).

After the Day 1 visit, all subjects will continue to return to the site on an outpatient basis for the study visits and procedures as identified in [Appendix C](#). Subjects could also return to the site for an unscheduled study visit for additional safety assessments if the investigator or sponsor feels it is necessary. Sites should ensure that subjects adhere to the study visits listed in [Appendix C](#). Subjects who cannot complete their study visit per the visit schedule should ensure they do not run out of study drug prior to their next study

visit. Study drug compliance is critical to ensure adequate drug exposure and optimal treatment outcome.

Virologic failure criteria will be evaluated and applied by the Investigator as detailed in Section 5.4.1.1.

Subjects who prematurely discontinue from the Treatment Period should return for a Treatment Discontinuation Visit and undergo the study procedures as outlined in [Appendix C](#) and as described in Section 5.5.1. Ideally, this should occur on the day of study drug discontinuation, but is recommended to be no later than 2 days after their final dose of study drug and prior to the initiation of any other anti-HCV therapy if applicable. Following completion or premature discontinuation of study drug treatment, all subjects in either Part 1 or Part 2 will be followed in the associated Post-Treatment Period of Part 1 or Part 2.

